The ongoing intervention questionnaire has been adapted from the United States Army Medical Command (MEDCOM) behavioral health intake form. The two questions asked request participants to explain the types of services they currently receive (i.e., alcohol and drug, community behavioral health, chaplains, etc.) and the type of therapy they are attending (i.e., individual, couples, family, or group).

The suicidality measure is comprised of items from other scales. Items 1-4 are from the Depression Symptom Index-Suicidality Subscale by Metalsky & Joiner⁸⁴, 1997; 5-6 created by Joiner and Gutierrez, 7-8 from the Beck Scale for Suicide Ideation by Beck & Steer, 1991⁸⁵, 9-11 from the Beck Hopelessness Scale by Beck, Weissman, Lester, & Trexler, 1972⁸⁶, and 12-16 from the Interpersonal Needs Questionnaire by Van Orden et al., 2012⁸⁷. This assessment examines thoughts about killing oneself, the number of suicide attempts since the last suicide risk assessment, wish to live/die, and feelings of belongingness within relationships. This suicide assessment was recommended by Centers for Disease Control suicide researchers, is currently being used within DoD, and derives from 5 different validated assessments.

The REDCap survey will consist of a demographic questionnaire, a Partner Contact form, the *PTSD Checklist* (PCL)⁸¹, the *Alcohol Use Disorders Identification Test* (AUDIT)⁸², the Childhood Trauma Questionnaire (CTQ)⁸³, a suicidality measure, the *Revised Conflict Tactics Scale-2* (CTS-2),⁴⁴ the *Multidimensional Measure of Emotional Abuse* (MMEA)⁸⁰, the *Dyadic Adjustment Scale* (DAS)⁶⁹, an ongoing intervention questionnaire, and a Post-intervention Satisfaction assessment.

During baseline assessment, the demographics questionnaire, partner contact form, CTS-2 (time one), DAS, MMEA, PCL, AUDIT, ongoing intervention assessment, the suicidality measure, and CTQ will be given to the participants. At the post-intervention assessment, the partner contact form, CTS-2 post-intervention, DAS, MMEA, PCL, AUDIT, ongoing intervention assessment, the suicidality measure, and post-intervention satisfaction measures will be given. At the 3-month follow up, partner contact, the CTS-2 post-intervention, DAS, MMEA, AUDIT, ongoing intervention assessment, the suicidality measure, and PCL will be assessed.

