Participants (service members and partners) will separately receive remuneration of a \$50 Visa Gift Card or a \$50 check sent to their address for completion of each assessment. Due to military compensation restrictions, and to ensure no conflict, if the service member is active duty, they may only be compensated if they fill out their surveys while on off-duty or on leave status.

(h) Intervention after Completion of Trial

Following the completion of the final assessment, all participants assigned to the *SP* condition will be offered the opportunity to participate in a *SAH-C* group. This participation would be entirely voluntary and would involve no further assessment or remuneration.

(6) Measures

(a) Outcome Measures

Outcome assessments are identical to those from Phase 1, though the assessment window for Phase 2 assessments refers to the prior three months. Data collected will include demographics questionnaire, partner contact form, PCL, AUDIT, Post-Intervention satisfaction, suicidality measure, MMEA⁸⁰, CTS2⁴⁴, ongoing intervention questionnaire, and DAS⁶⁹.

(b) Intervention Compliance Measure

Session Attendance will be measured as the total number of group sessions attended by each client.

(7) Stakeholder Meetings

Stakeholder meetings will be held to discuss study performance and needs of the study, such as discussions related to study recruitment, barriers to participation, and dissemination of research findings.

(c) Intent-to-Treat (ITT) versus “Adequate Dose” Analyses

An ITT philosophy will be strictly adopted. Experts in clinical trials have noted that no consensus exists about how missing data should be handled in ITT analyses, and different imputation approaches result in various potential biases. Thus, there is no single definition of ITT, and the phrase carries different meanings for different researchers.^{87,88} Therefore, every effort will be made to collect complete outcome data for all randomized participants, regardless of their intervention completion. As discussed in section D.3.7., measurement losses are expected to be relatively small due primarily to the use of tracking procedures, as well as the relatively short follow-up assessment periods.

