assumed to be a function of observed covariates and previously measured outcomes, but not unobserved outcomes). Based on such considerations, this type of an approach has been recommended for analyzing outcomes in prevention trials as it is generally more powerful than traditional repeated measures analyses of variance.⁹¹ In the current project it is of interest to model person-specific effects (i.e., time course for each participant), as well as the variation of responses between individuals. In addition, because of the suspected intraclass correlation between individuals nested within intervention groups, couples, and perhaps intervention site, these variables will be treated as fixed effects in the analyses. Time will be modeled as a random effect, and condition (*SAH-C* and *ST*) will be a fixed effect. Change in intervention outcomes over time and differences between the conditions over time (intervention by time interactions) will be examined. The primary effect size for the study will be derived from the random regression analyses, and specifically the intervention by time interaction, which will compare the two groups across intervention and follow ups. There are covariates that are *a priori* hypothesized to be associated with intervention outcomes, including socioeconomic status and education, and these will be included in follow-up analyses to significantly reduce error variance.

(e) Exploratory Analyses

Differences between the two group conditions in participant intervention compliance (Aim 2) will be explored by examining condition differences in session attendance using ANOVAs.

(f) Qualitative Analytic Strategy and Data Integration

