Inclusion criteria are as follows: (a) couples (heterosexual and same-sex dyads) must be in an intimate relationship; (b) participants and their partners must be over the age of 18, due to our emphasis on adult IPA, and so that all participants will be legally able to provide consent without parental involvement; (c) both members of the couple report no occurrence of physical IPA in the past 3 months; (d) at least one member of the couple reports at or below a score of 100 on the Dyadic Adjustment Scale (DAS), a cutoff score used to distinguish relationship distress, or they report the presence of psychological aggression in the past three months; and (e) both members of the couple provide research consent. Pregnant women are eligible to participate in this study. Research indicates that pregnant women may be at increased risk for intimate partner victimization. Thus, violence prevention interventions may be particularly applicable and important for this group. Potential participants will be excluded on the basis of reading difficulties that preclude valid completion of the assessment instruments.

Gender Inclusion

The couples-based interventions studied make it likely that equal numbers of men and women will participate. However, we will make no exclusions related to gender/gender identity, and same-sex couples are also eligible for participation.

Minority Inclusion

Across the study sites, 70% of potential participants are Caucasian, 20% are African American, and 10% are of another ethnicity.

(b) Sources of Materials

Data will be obtained from subjects from self-report measures completed through the online data collection tool, REDCap. Data will not be collected from routine medical care. All data gathered and analyzed will be obtained for this specific study. Study participation will not be documented in participants' electronic medical records.

(c) Potential Risks

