All appropriate service members aged 18 or older, with partners over the age of 18, reporting no occurrence of physical IPA over the prior 3 months in their relationship will be invited with their partners to participate in a screening to determine appropriateness for group intervention and assess study eligibility. Members of the couple will arrive together but be screened separately to ensure confidentiality and safety. Both members of the couple will be administered the DAS to assess relationship distress, partner contact frequency, the MMEA for emotional abuse, the PCL to screen for PTSD, the AUDIT to screen for alcohol use, the CTQ for child abuse and neglect history, the CTS-2 to assess lifetime history of IPA in their current relationship, the suicidality measure, and the demographics questionnaire. If either participant fails to meet study eligibility requirements, the couple's participation will end. If IPA is reported by either partner, the trained psychoeducational facilitator will separately inform them that they are not eligible for this study, and will assess the victim or victims' perceptions of safety, discuss safety planning with the victim(s) (e.g., packing a small bag with a change of clothes and important papers in the event that s/he needs to escape), and will provide them with local contact information for Victim Advocacy services. Victims will be educated by the Victim Advocate about reporting options which include restricted reporting.

In the event a participant endorses suicidal ideation, the facilitator will conduct safety planning and offer a referral to FAP for additional assistance. If there is imminent threat, the facilitator will inform FAP to conduct a formal suicide assessment or accompany the participant to the emergency room. Additionally, if they have a counselor we will direct them to contact their counselor immediately.

(b) Protection Against Risk

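### The screening CTS-2 is given a lifetime window while Phase 2 assessments and eligibility use three months, and the plan does not say which score is the baseline

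*Combined protocol and SAP*

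**What the plan says.** Five places in the combined protocol and SAP bear on the recall window of the CTS-2.

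- Screening procedures, in (9)(a): each partner completes "the CTS-2 to assess lifetime history of IPA in their current relationship". The same paragraph continues: "If IPA is reported by either partner, the trained psychoeducational facilitator will separately inform them that they are not eligible for this study".
- Outcome Measures, (6)(a): "the assessment window for Phase 2 assessments refers to the prior three months". No exception is made for baseline.
- Inclusion/Exclusion Criteria, in (8)(a): criterion (c) is that "both members of the couple report no occurrence of physical IPA in the past 3 months". Criterion (d) admits a couple on a low DAS score, or if "they report the presence of psychological aggression in the past three months".
- Questionnaires: the baseline list opens with "demographics questionnaire, partner contact form, CTS-2 (time one), DAS, MMEA, PCL, AUDIT". Later visits use a CTS-2 form labelled post-intervention. No recall window is given for either form.
- Primary Data Analyses, (d): the primary effect size comes from the random regression, "specifically the intervention by time interaction, which will compare the two groups across intervention and follow ups". The section does not say which CTS-2 score is the baseline, or whether baseline enters as an outcome or a covariate.

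**The concern.** A lifetime count and a three-month count are different variables, even on the same items. If the only pre-intervention CTS-2 asks about the whole relationship and every later one asks about three months, change from baseline partly measures the change of window. Three things are then at stake:

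- the meaning of change over time within each arm, which Primary Data Analyses also sets out to examine;
- the precision of the intervention-by-time contrast, because a wider-window baseline is likely to be more variable and less correlated with follow-up;
- eligibility, which is defined on three months but would be checked with an instrument described as lifetime.

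A window used at baseline cannot be reliably reconstructed afterwards, so this has to be settled before data collection.

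**Working it through.** **1. Is the screening CTS-2 the baseline CTS-2?** The baseline list under Questionnaires has ten items: demographics, partner contact, CTS-2, DAS, MMEA, PCL, AUDIT, ongoing-intervention questionnaire, suicidality and CTQ. Screening procedures lists nine of them; only the ongoing-intervention questionnaire is absent. No second pre-intervention CTS-2 is described. The likely reading is one administration, but the text does not say so.

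**2. The plan's own power figure.** Power Analysis states power above .9 with N = 280 (140 couples), d = .5, 20% attrition, within-subjects correlation .70 and two-tailed .05. The exact GEESIZE set-up is not given.

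- Individuals: 280 × .8 / 2 = 112 per arm; power .963.
- Couples: 140 × .8 / 2 = 56 per arm; one post-only comparison gives .754, and change from a baseline correlated .70 gives .927.

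The figure reproduces as a lower bound for individuals. For couples with a single follow-up, it depends on a baseline that correlates .70 with follow-up.

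**3. Precision of the change contrast.** Take the mean of the three post-baseline visits minus baseline. Let σ be the three-month SD, k the ratio of baseline SD to σ, and r′ the correlation of baseline with each later score. Later scores correlate .70 with each other.

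Variance / σ² = (1 + 2 × .70)/3 + k² − 2r′k = .80 + k² − 2r′k

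| Baseline | k | r′ | Variance / σ² |
|---|---|---|---|
| Same window (plan's r) | 1 | .7 | .80 + 1 − 1.40 = .40 |
| Lifetime (assumed) | 1 | .5 | .80 + 1 − 1.00 = .80 |
| Lifetime (assumed) | 1.5 | .5 | .80 + 2.25 − 1.50 = 1.55 |
| Lifetime (assumed) | 2 | .5 | .80 + 4 − 2.00 = 2.80 |

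The lifetime values of k and r′ are assumptions; the documents give neither.

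**4. The same comparison with baseline as a covariate.** The residual variance is .80 − r′², whatever k is: .80 − .49 = .31 at r′ = .7 and .80 − .25 = .55 at r′ = .5. This ratio is about 1.8, against 3.9 to 7 for raw change (1.55/.40 to 2.80/.40).

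**5. Power, 56 couples per arm, d = .5, one follow-up.** The change-score SD is √(1 + k² − 2r′k).

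- Same window, r′ = .7: SD .775, power .93; covariate-adjusted .96.
- k = 1.5, r′ = .5: SD 1.323, power .52; covariate-adjusted .86.
- k = 2, r′ = .5: SD 1.732, power .33; covariate-adjusted .86.

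**6. Bias under the null.** In 20,000 simulated trials there were 56 couples per arm, no treatment effect, a mean of 0.5 incidents per three months and a lifetime baseline assumed to span 12 such windows. The between-arm test of change rejected 4.6% of the time. Both arms showed a mean fall of 5.5 incidents, which is simply 0.5 × (12 − 1).

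**7. Physical IPA is different.** Criterion (c) makes the reported three-month baseline zero, or nearly so, for enrolled couples. Then k is about 0, the common-window variance is .80 rather than .40, and a .70 correlation with baseline has no meaning. If the screening exclusion is applied to lifetime physical IPA, the lifetime baseline is zero too and there is no loss.

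**8. Eligibility.** Consider two couples.

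- Physical IPA earlier in the relationship, none in the past three months, low DAS: meets criteria (c) and (d), but has IPA to report on a lifetime CTS-2 and so meets the screening exclusion as worded.
- Psychological aggression only, within three months: qualifies under (d). Read literally, the screening exclusion also removes this couple, because the primary hypotheses count psychological IPA as a form of it.

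**The case against.** The strongest reply is that Outcome Measures already settles the matter. Its window covers Phase 2 assessments without exception, and its list includes the demographics form, which Questionnaires schedules only at baseline. Read literally, the modelled baseline is a three-month score and the lifetime wording describes a screening or history item. The schedule of assessments in Figure 9, not available here, might show screening and baseline as separate. This stands as far as it goes: nothing says that the lifetime score enters the model. But if the two are separate, the text never describes the three-month pre-intervention CTS-2. If they are the same, two sections give it different windows.

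A reader might infer that the randomized comparison is biased. It is not under the null, because the window difference is common to both arms. A reader might also carry the 3.9- to 7-fold variance ratio across to every primary outcome. That is not supported: it rests on assumed values and on raw subtraction of baseline, and it does not fit physical IPA. Relationship satisfaction uses the DAS and psychological IPA is also measured by the MMEA; the screening text attaches no lifetime window to either.

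On eligibility, couples are invited to screening only if they report no physical IPA over the prior three months, and criterion (c) does not name the CTS-2 as its source. A lifetime report of none also satisfies it. So it would be too strong to say that criterion (c) cannot be checked at all; only a positive lifetime report is uninformative.

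**Conclusion.** The contradiction is real and should be corrected. The apparently sole pre-intervention CTS-2 is described as lifetime, against three-month windows for Phase 2 assessments and for eligibility. Mixing of windows in the primary model is a conditional risk, present only if the screening score is the modelled baseline. In that case the consequences are an artefactual fall in both arms and lost precision, mainly for CTS-2 psychological IPA. The amount cannot be fixed from the documents. The calculated range depends on assumed SD ratios of 1.5 to 2 and a correlation of .5, and most of the loss goes if baseline is a covariate.

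The eligibility conflict needs no numerical assumptions. The screening exclusion has no window or type, while the inclusion criteria exclude only physical IPA in the past three months and let psychological aggression qualify a couple.

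**What to change.** Reconcile Questionnaires, Outcome Measures, Inclusion/Exclusion Criteria and Screening procedures:

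- State that the time-one CTS-2 is collected and scored on the prior three months.
- State that this score is used to check the three-month eligibility criteria and is the baseline value in the primary model.
- Label any lifetime item as separate and descriptive.
- Align the screening exclusion with the inclusion criteria, so that both give the same window and type of IPA.

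The cost is slightly longer wording on the baseline form and a few protocol sentences. The sample size, visits and instruments do not change.

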A Hybrid Type-I Implementation-effectiveness research design will allow the research team, comprising investigators with expertise in intervention development, efficacy and effectiveness research, and implementation science, to simultaneously investigate the effectiveness of *SAH-C* in a military population while identifying any barriers to implementation that would need to be addressed before *SAH-C* could be successfully implemented on a larger scale. The study site for this proposed effort is Joint Base Lewis McChord, Washington.

The primary hypotheses are that those receiving *SAH-C* will evidence greater reductions in physical and psychological IPV, and greater increases in relationship satisfaction, relative to those receiving *Supportive Prevention* across the follow up time points.

(c) Specific Objectives.

AIM 1: To test the effectiveness of *SAH-C* for military couples on an installation, we will conduct a randomized trial comparing 10 sessions of *SAH-C* to 10 sessions of *Supportive Prevention (SP)* under representative conditions, with 140 couples who are at risk for the development of IPA (risk is established if at least one member of the couple reports at or below a score of 100 on the Dyadic Adjustment Scale (DAS), a cutoff score used to distinguish relationship distress, or they report the presence of psychological aggression in the past three months). This aim will be fulfilled by accomplishing the following subaims:

Subaim 1.1: To compare the frequency of physical IPA perpetration of both members of the couple across conditions as reported by service members and their collateral relationship partners at post-intervention and two 3-month follow ups.

Subaim 1.2: To compare the frequency of psychological IPA perpetration of both members of the couple across conditions as reported by service members and their collateral relationship partners at post-intervention and two 3-month follow ups.

Subaim 1.3: To compare relationship satisfaction across conditions as reported by service members and their collateral relationship partners at post-intervention and two 3-month follow ups.

AIM 2: To explore differences in compliance factors across conditions, we will compare session attendance.

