The PCL is widely used as an assessment for screening individuals for PTSD and monitoring change across time. This questionnaire includes a list of potential responses an individual may have following an extremely stressful experience⁸¹.

The AUDIT is a widely used screening tool to assess alcohol consumption and alcohol-related behaviors

The CTS-2 is the most widely used measure of IPA, with excellent internal consistency reliability, content validity, and construct validity.^{44,66} The measure assesses physical, psychological, and sexual aggression in intimate relationships. Respondents report on the frequency of each item for themselves and their partners. Combined partner reports are used to reduce IPA underreporting.

Because the CTS-2 assesses a fairly limited number of psychologically abusive behaviors, the Multidimensional Measure of Emotional Abuse (MMEA) will also be administered to assess psychological IPA.⁹⁶

The DAS is appropriate for use with both married and cohabitating couples. In addition to a global satisfaction score, this 32-item measure consists of four subscales: Dyadic Consensus, Affectional Expression, Dyadic Satisfaction, and Dyadic Cohesion. Several studies provide evidence for this measure's strong psychometric properties.⁶⁷⁻⁶⁹

The post-intervention satisfaction questionnaire asks questions to determine barriers and facilitators of the program. This information will be used to make adjustments to the program if necessary.

The partner contact form consists of a single item assessing the frequency of contact with the participant's partner.

In addition to the self-report questionnaires, a collateral contact form will be completed by each individual to ensure research staff will be able to contact the individual if they move away prior to the final time point. The form includes contact information for themselves as well as up to three others that research staff can contact if there is difficulty getting in contact with the participants.

Intervention and Integrity Measure Refinement

To facilitate the rapid integration of the information into the refinement of the intervention and materials, meeting summaries will be content analyzed using a rapid coding technique based on methods of Sobo et al.^{70,71}

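### The screening text makes a couple ineligible for reported IPA without giving a type or recall window, which conflicts with the inclusion criteria and must be reconciled

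*Combined protocol and SAP*

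**What the plan says.** **Formal criteria, section (8)(a), Inclusion/Exclusion Criteria.** Criterion (c) requires that "both members of the couple report no occurrence of physical IPA in the past 3 months". Criterion (d) requires risk, shown either by a DAS score of 100 or less in at least one member, "or they report the presence of psychological aggression in the past three months". Aim 1 in section (1)(c) defines risk by the same two routes.

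**Screening procedures, section (9)(a).** The paragraph opens by inviting couples "reporting no occurrence of physical IPA over the prior 3 months in their relationship". It lists the screening battery, including "the CTS-2 to assess lifetime history of IPA in their current relationship". A general sentence then ends participation for any couple that fails the eligibility requirements. The next sentence reads: "If IPA is reported by either partner, the trained psychoeducational facilitator will separately inform them that they are not eligible for this study". That same sentence goes on to the safety assessment and safety planning.

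**Meaning of the terms.** Of the CTS-2, the questionnaire section says: "The measure assesses physical, psychological, and sexual aggression in intimate relationships". Subaim 1.2 is "To compare the frequency of psychological IPA perpetration of both members of the couple across conditions", and Table 1 lists psychological rows under types of IPA. Section (6)(a) gives a three-month window for Phase 2 assessments.

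**The concern.** The sentence that tells staff whom to declare ineligible does not match the formal criteria. The mismatch has two parts.

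- **Window.** Criterion (c) looks back 3 months. The screening sentence has no window, and the instrument named just before it covers the lifetime of the relationship.
- **Type.** Criterion (c) concerns physical IPA only, and criterion (d) treats psychological aggression as qualifying. The screening sentence says only IPA, a term the protocol elsewhere uses to include psychological IPA.

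At stake is who enters the trial. If staff resolve the wording differently from one another, the enrolled population cannot be defined from the protocol. If they follow it literally, couples who qualify under criterion (d) are sent away, and no later analysis can restore them. The primary hypothesis on psychological IPA would suffer most, because it predicts a reduction from a baseline that the rule would hold near zero.

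**Working it through.** The plan states no figure on this point, so there is none to reproduce. The check has two steps.

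**1. Apply each rule to the same couples.**

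| Couple reports | Section (8)(a) | Section (9)(a), literal |
|---|---|---|
| Physical IPA in past 3 months | Ineligible | Ineligible |
| Physical IPA only before that window; DAS ≤ 100 | Eligible | Ineligible if lifetime reports count |
| Psychological aggression in past 3 months; no physical IPA | Eligible | Ineligible |
| No IPA of any kind; DAS ≤ 100 | Eligible | Eligible |

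The rules agree on the first and last rows. Reading IPA as physical IPA repairs the third row but not the second. A lifetime report also does not by itself date the event, so it cannot establish whether the 3-month criterion is met. The documents give no figure for couples in the second row.

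**2. Size the third row from Table 1.** The inputs are baseline (T1) CTS psychological IPA in the prior randomized trial. For a non-negative score with mean m and variance v, the Cauchy–Schwarz inequality gives

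share with score above 0 ≥ m² / (m² + v), with v = SD² × (n − 1)/n.

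This needs no assumption about the shape of the distribution.

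| Perpetrator, arm | m (SD), n | m² | v | Minimum share above 0 |
|---|---|---|---|---|
| Veteran, SAH-C | 30.76 (25.9), 41 | 946.2 | 654.4 | 946.2/1600.6 = 0.591 |
| Veteran, SP | 37.94 (26.7), 37 | 1439.4 | 693.6 | 1439.4/2133.1 = 0.675 |
| Partner, SAH-C | 30.29 (24.3), 41 | 917.5 | 576.1 | 917.5/1493.6 = 0.614 |
| Partner, SP | 32.84 (21.5), 37 | 1078.5 | 449.8 | 1078.5/1528.2 = 0.706 |

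Rounded down, at least 59%, 67%, 61% and 70% of members had a non-zero score. Using SD² without the (n − 1)/n factor gives 0.585 to 0.700, which is the same picture.

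One report by either partner rejects the couple, so the share of couples is at least the larger of the two member shares in each arm: 61% (SAH-C) and 70% (SP). The documents do not state the recall window behind Table 1, but a lifetime window cannot give a smaller share than a shorter one.

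**The case against.** The strongest reply is that context settles the meaning. The paragraph opens with the 3-month physical limit. The general eligibility sentence just before the disputed one points back to the formal criteria, so the disputed sentence may only describe how to notify and protect couples after a disclosure. Its content (safety planning, escape, victim advocacy) fits physical violence. Criterion (d) speaks of psychological aggression rather than IPA, and Aim 1 treats that aggression as a marker of risk for IPA. Staff holding both sections would probably notice that a literal reading voids half of criterion (d).

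Much of this stands, and physical IPA is the more natural reading. It does not close the gap. The opening limit describes who is invited to screening. Because the general sentence already covers failures of criterion (c), the next one can be read as a further trigger. Subaim 1.2 and Table 1 both count psychological IPA as IPA. The window stays open even on the physical reading.

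A reader might infer that the protocol rejects couples on a lifetime CTS-2. It does not say so: the ineligibility sentence names neither the instrument nor a lifetime window, and the link comes only from the battery listed shortly before it. Nor do the documents show that staff applied, or would apply, the literal rule.

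**Conclusion.** The two sections conflict as written and need to be reconciled. The window conflict holds on either reading of IPA; its size is unknown. The type conflict depends on a literal reading. In a population like the prior trial's, that reading would reject most couples (at least 61% and 70% by arm) and leave little room to show a reduction in psychological IPA.

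Three stronger conclusions are tempting but unsupported.

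- **That all at-risk couples are lost.** Couples with DAS at or below 100 and no reported IPA remain eligible under both sections.
- **That both IPA outcomes are pushed to the floor by this sentence.** Criterion (c) already makes low baseline physical IPA a feature of the design. In the prior trial, where physical IPA was an exclusion for Veterans, their baseline means were only .44 and .14. The added floor effect is mainly on psychological IPA.
- **That recruitment would fail.** Section (5)(f) cites a pool of more than 1,600 couples. Falling below 140 would need a rejection share above 1 − 140/1600 = 91%, even if every remaining couple enrolled. The bound does not reach that. A negative binomial with the Table 1 moments would put the non-zero share at roughly 99%, but the documents do not give the distribution.

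**What to change.** Reconcile the screening text in section (9)(a) with the criteria in section (8)(a) on both the type of IPA and the recall window. One way is for the ineligibility sentence to cross-refer to criterion (c). The sponsor decides which rule governs. State which CTS-2 recall window establishes the 3-month criterion, and how the lifetime version used at screening relates to the three-month window in section (6)(a).

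Ineligibility and the safety response now share one sentence and one trigger. Give them separate triggers, because narrowing the shared one to align eligibility would also narrow who receives the safety response.

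The cost is a small edit to the protocol and a matching edit to the screening script. Sample size is unaffected.
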